##### **17.4.6.2 Analysis**

For this outcome see section 17.4.2.2 for analysis details. In addition to this, effect estimates, 95% CIs and a p-value at T18 should be reported.

#### **17.4.7 Core Outcome Measures Index (COMI) at baseline, and at 18, 30, 42 and 54 weeks after randomisation**

##### **17.4.7.1 Derivation**

Core Outcome Measures Index scores can be found in patient questionnaire booklet 1 (Questions 1-5). Pain intensity, function and symptom-specific and general well-being are measured using a 1-5 point Likert scale. Disability measurements for social life and work are measured in days of work incapacity/restricted activity over the past 4 weeks and could range from 0 to 28. The COMI score is calculated by recoding responses as in Table 17.4.7.1(a) and taking the average of all items. COMI scores should only be calculated if all items are present.

The date that the patient questionnaire (booklet 1) has been completed is also required for this outcome; see section 17.4.1.1 for details on how to derive missing questionnaire completion dates.

**Table 17.4.7.1(a)**

Item no (MACRO variable)	Recoding
COMI1AC	1 = Not at all bothersome 2 = Slightly bothersome 3 = Moderately bothersome 4 = Very bothersome 5 = Extremely bothersome
COMI1BC	1 = Not at all bothersome 2 = Slightly bothersome 3 = Moderately bothersome 4 = Very bothersome 5 = Extremely bothersome
COMI2C	1 = Not at all 2 = A little bit 3 = Moderately 4 = Quite a bit 5 = Extremely
COMI3C	1 = Very dissatisfied 2 = Somewhat dissatisfied 3 = Neither satisfied nor dissatisfied 4 = Somewhat satisfied 5 = Very satisfied
COMI4I	1 = 0 days 2 = 1-7 days 3 = 8- 14 days 4 = 15-21 days 5 = > 22 days
COMI05I	1 = 0 days 2 = 1-7 days 3 = 8- 14 days 4 = 15-21 days 5 = > 22 days

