**Table 17.4.5.1(a)**

Item no (MACRO variable)	Recoding
COMI6C	1= Very satisfied 2 = Somewhat satisfied 3 = Neither satisfied nor dissatisfied 4 = Somewhat dissatisfied 5 = Very dissatisfied
COMI7C	1= Very satisfied 2 = Somewhat satisfied 3 = Neither satisfied nor dissatisfied 4 = Somewhat dissatisfied 5 = Very dissatisfied

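### SAP Table 17.4.7.1(a) codes COMI3C in the opposite direction to the other five COMI items, so the averaged score, if programmed as written, shrinks any between-arm difference that COMI3C shares

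*SAP*

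**What the plan says.** SAP section 17.4.7.1 gives the scoring rule: "The COMI score is calculated by recoding responses as in Table 17.4.7.1(a) and taking the average of all items". It adds that "COMI scores should only be calculated if all items are present". It does not say whether a high COMI is good or bad, whereas section 17.4.6.1 does state the direction of the Roland-Morris score.

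Table 17.4.7.1(a) sets the codes for the six items:

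- The two pain items, COMI1AC and COMI1BC, run from no bother (code 1) to extreme bother (code 5).
- Item COMI2C runs from none (code 1) to extreme (code 5).
- Item COMI3C is scored in this order: "1 = Very dissatisfied 2 = Somewhat dissatisfied 3 = Neither satisfied nor dissatisfied 4 = Somewhat satisfied 5 = Very satisfied".
- The two day items, COMI4I and COMI05I, run from no days (code 1) to the longest band of days (code 5).

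The two satisfaction items that form the separate treatment-satisfaction score (COMI6C and COMI7C, Table 17.4.5.1(a)) start from the other end: "1= Very satisfied 2 = Somewhat satisfied 3 = Neither satisfied nor dissatisfied".

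Under sections 17.4.7.2 and 17.4.2.2 the COMI score goes into the repeated-measures model, and an effect estimate, 95% CI and p-value are also reported at week 18.

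**The concern.** An unweighted mean is a severity score only if all its items point the same way. Here five items add to the score as the patient gets worse, and COMI3C subtracts from it. If a treatment helps on all six items, the gain on COMI3C cancels part of the gain on the others, and the reported difference between arms is too small.

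COMI is a named secondary outcome in protocol section 4.2 and SAP section 9.2. The planned quality control is not designed to catch a scoring fault in it: SAP section 21 has an independent statistician re-program the primary analysis and the safety data, and COMI is neither.

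There is a smaller gap in the same table. The day items may take any value from 0 to 28 (section 17.4.7.1), but the last two bands are "4 = 15-21 days 5 = > 22 days", which leaves exactly 22 without a code.

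**Working it through.** The documents give no COMI figure to reproduce: no expected difference, no SD and no power. The check therefore applies the table directly.

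**1. Direction of each item, read from the response labels**

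| Item | Code 1 | Code 5 | Rises with |
|---|---|---|---|
| COMI1AC, COMI1BC | not bothersome | extremely bothersome | worse status |
| COMI2C | not at all | extremely | worse status (item text not in the documents) |
| COMI3C | very dissatisfied | very satisfied | better status |
| COMI4I, COMI05I | 0 days | top day band | worse status |

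**2. Attainable range**

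Items are taken in table order, with a patient who is consistently best or worst on all six.

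- Best, as written: (1 + 1 + 1 + 5 + 1 + 1)/6 = 10/6 = 1.67. With COMI3C replaced by 6 - x: 6/6 = 1.00.
- Worst, as written: (5 + 5 + 5 + 1 + 5 + 5)/6 = 26/6 = 4.33. With COMI3C replaced by 6 - x: 30/6 = 5.00.

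The width falls from 4.00 to 2.67, a loss of one third.

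**3. Effect on the between-arm difference**

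Let the arms differ by d on each of the five aligned items, and by k × d on COMI3C in the same clinical direction. Then:

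- as written: (5 - k)d/6
- aligned: (5 + k)d/6
- ratio: (5 - k)/(5 + k)

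| k (assumed) | As written | Aligned | Ratio |
|---|---|---|---|
| 0 | 0.833d | 0.833d | 100% |
| 0.5 | 0.750d | 0.917d | 82% |
| 1 | 0.667d | 1.000d | 67% |
| 2 | 0.500d | 1.167d | 43% |

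For these values the bias is towards zero or absent. A negative k, meaning that COMI3C moves against the other items, would inflate the difference instead.

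**4. Day bands**

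Passing each integer from 0 to 28 through the bands leaves one value uncoded, 22, in both COMI4I and COMI05I. Coding such an answer 4 or 5 changes that patient's score by 1/6 = 0.17 per item.

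**The case against.** Several points can be said for the plan, and some of them stand.

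- **The wording of COMI2C and COMI3C is not in the documents.** The questionnaire is a separate document, so direction is inferred from the response labels. This stands, and it is why the recode should follow a check of the booklet. The labels still make reversal the natural reading: nothing suggests that greater satisfaction should raise a score that also rises with pain and lost days.
- **COMI6C and COMI7C prove nothing about COMI3C.** They belong to a different score and never enter the COMI mean. This stands. Their coding shows only that the SAP does not use one satisfaction convention throughout.
- **A programmer may reverse the item anyway.** The result would then be right but would depart from the SAP, so the text needs correcting either way.
- **The loss of signal is smaller than the loss on the raw scale.** The SD shrinks too. With k = 1, equal item variances and equal inter-item correlation r, the SD ratio is √((6 + 10r)/(6 + 30r)) = 0.77, 0.72 and 0.69 for r = 0.3, 0.5 and 0.7. The standardised effect is then 0.667 divided by these, that is 0.86, 0.92 and 0.96 of its aligned value. This stands as an illustration; the documents support no particular r.

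A reader might also infer more than the documents support:

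- That the COMI difference will be a third too small. That is the single case k = 1.
- That a stated 90% power is eroded. Protocol sections 9.4 and 9.4.2 give that figure for the ODQ only, so no COMI power loss can be calculated.
- That a patient answering 22 days loses the COMI score, or that this gap biases the comparison. The rule asks for items to be present, and 22 is a present answer. A programmer could well put it in the top band, and the number of such patients is unknown.

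**Conclusion.** The scoring rule is wrong as written. One of the six averaged items runs against the other five, and nothing elsewhere in the protocol or SAP corrects it. The compressed range of 1.67 to 4.33 follows from the table alone. The attenuation of the between-arm difference depends on two conditions: that the program follows the table literally, and that the arms differ on COMI3C in the same clinical direction as on the other items. Given both, the size depends on the relative shift in COMI3C, which is unknown.

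The score still orders consistent patients from best to worst, so it is a contaminated severity scale and not a meaningless one. For shifts in the same clinical direction over the range shown, the error hides a difference and does not create one. The 22-day gap is real but minor, and its effect on the comparison cannot be sized. The consequence is confined to one secondary outcome; the primary ODQ analysis does not use this score.

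**What to change.** 1. Check the wording and response order of COMI3C (and COMI2C) against Patient Questionnaire Booklet 1 and the COMI source in the SAP's reference list (reference 12).
2. Subject to that check, change the COMI3C row of Table 17.4.7.1(a) so that 1 is Very satisfied and 5 is Very dissatisfied, or state that the item enters the mean as 6 - x. Apply it at baseline and at every follow-up, since baseline COMI is a covariate.
3. State in section 17.4.7.1 that a higher COMI means worse status.
4. Minor: change code 5 of COMI4I and COMI05I to 22-28 days.

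The cost is a few lines of the SAP, a change-control entry and the matching code. No new data are needed.

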#### **17.4.7.2 Analysis**

For this outcome see section 17.4.2.2 for analysis details. In addition to this, effect estimates, 95% CIs and a p-value at T18 should be reported.

### **17.4.8 Work status at follow-up**

#### **17.4.8.1 Derivation**

This includes information found on CRF “Form 1: Baseline & Eligibility” on page 3 and CRF “Form 4: Follow up visits” on page 1. If a patient was unable to attend work at baseline and the date they stopped and returned to work at baseline and follow-up respectively is stated, then the number of work days lost under the assumption each patient works 5 out of 7 days per week should be calculated.

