### **4.2 Secondary Endpoint(s)**

- a. ODQ at 30, 42 and 54 weeks after randomisation
- b. Numerical rating scores for leg pain at baseline, and at 18, 30, 42 and 54 weeks after randomisation
- c. Numerical rating scores for back pain at baseline, and at 18, 30, 42 and 54 weeks after randomisation
- d. Likert Scale to assess patient treatment satisfaction at 18, 30, 42 and 54 weeks after randomisation
- e. Modified Roland-Morris outcome score for sciatica at baseline, and at 18, 30, 42 and 54 weeks after randomisation
- f. Core Outcome Measures Index (COMI) at baseline, and at 18, 30, 42 and 54 weeks after randomisation
- g. Work status (return to work and work days lost if applicable)
- h. Cost-effectiveness, expressed as the incremental cost per quality-adjusted life-year (QALY) based on the EQ-5D-5L

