## 9.6 Analysis Plan

The primary outcome (ODQ score at 18 weeks post-randomisation) will be compared between groups using a linear regression model, adjusted for the stratification variable centre, baseline ODQ score, and possibly other (specified in advance) variables considered to be potential confounders. Analysis of secondary outcomes will use similar methods, with logistic regression analyses used where appropriate. The intention to treat principle will be applied as far as is practically possible. The analysis set for the primary outcome will include all participants with an ODQ score at 18 weeks. Reasons for missing primary outcome data will be assessed, blind to treatment allocation, as to whether they are informative of likely outcome. Participants with non-informative reasons for missingness will be excluded from the primary analysis set. Sensitivity analyses will be carried out using multiple imputation to assess the robustness of the analysis to missing primary outcome data.

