#### **17.4.8.2 Analysis**

Firstly, a summary of the following will be presented:

- number of patients that are employed/not employed at each time point by treatment group (Baseline, week 18 and week 54)
- of those patients who are employed, the number of patients that are off work/at work by treatment group
- of those patients who are employed and unable to work, the number of patients that returned to work at 18 and 54 weeks
- Mean, SD, median, IQR and range of the work days lost where applicable

Secondly, work status (at work or off work) at 18 or 54 weeks post randomisation will be compared between groups using a chi-square test. The chi-square statistic and p-value will be presented. In addition to this, the relative risk and 95% confidence interval will be presented.

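### Work days lost are derived only for patients off work at baseline who later return, so the summary by arm ignores non-returners and shrinks a difference in return rates

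*SAP*

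**What the plan says.** Protocol 4.2 and SAP 9.2 list work status as a secondary outcome with two parts, return to work and work days lost, the latter if applicable.

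SAP 17.4.8.1 sets the derivation. A value exists only where the patient was "unable to attend work at baseline and the date they stopped and returned to work at baseline and follow-up respectively is stated"; the number of days "under the assumption each patient works 5 out of 7 days per week should be calculated".

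SAP 17.4.8.2 sets the reporting. Days lost appear as "Mean, SD, median, IQR and range of the work days lost where applicable", with no test, effect estimate or confidence interval. The same section reports, by arm, how many patients are employed at baseline, week 18 and week 54 and how many of the employed are at work or off work. It also reports, "of those patients who are employed and unable to work, the number of patients that returned to work at 18 and 54 weeks". The one formal comparison is that "work status (at work or off work) at 18 or 54 weeks post randomisation will be compared between groups using a chi-square test", with a relative risk.

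No other section supplies a value for a patient without a return date. SAP 17.1 analyses participants whose outcome was observed, and SAP 18 plans multiple imputation for the primary outcome only.

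**The concern.** Two groups receive no days-lost value: patients off work at baseline who have not returned by week 54 or last contact, and patients at work at baseline who go off work later, for instance after the procedure. The first group has the longest absences. Leaving it out makes inclusion in the mean depend on a success that occurs after randomisation, so the arms being summarised are no longer the randomised groups.

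The second group matters because Protocol 2.2 describes the injection as a day case and surgery as averaging two nights in hospital. Absence for recovery may therefore differ between arms.

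A published mean number of work days lost by arm will be read as a treatment comparison even without a test. Protocol 2.1 describes the patients as typically young working adults, so readers will look for this figure.

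**Working it through.** The plan states no figure for days lost, so there is nothing to reproduce. The check asks how the planned mean behaves as the share of non-returners changes.

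**Inputs from the documents.** Follow-up is 54 weeks from randomisation (Protocol 8.1). A week counts as 5 working days (SAP 17.4.8.1). Only patients with a return date enter (SAP 17.4.8.1).

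**Inputs assumed.** The number off work at baseline, the return times and the share who never return are not in the documents.

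**Illustration 1: fixed return times.** Assume 30 patients per arm off work at baseline, all of whom stopped 8 weeks before randomisation. A patient returning at week w has (8 + w) × 5 days. A patient not back by week 54, counted to that point, has (8 + 54) × 5 = 310 days, of which 54 × 5 = 270 fall after randomisation.

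- Arm A: 27 return at week 16 and 3 do not return. Planned rule: (8 + 16) × 5 = 120 days, n = 27. All patients: (27 × 120 + 3 × 310) / 30 = 139 days.
- Arm B, same return time: 18 return at week 16 and 12 do not return. Planned rule: 120 days, n = 18. All patients: (18 × 120 + 12 × 310) / 30 = 196 days.

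The planned rule shows no difference, while the full count differs by 196 − 139 = 57 days.

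If the returners in arm B instead come back at week 14, the planned rule gives (8 + 14) × 5 = 110 days against 120, and the full count gives (18 × 110 + 12 × 310) / 30 = 190 against 139. The order of the arms reverses, but only because arm B was also given faster returners. With week 14 held fixed, raising non-return in arm B from 10% to 40% moves its full count from 130 to 190 days and leaves its planned mean at 110.

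**Illustration 2: constant return rates.** Let p be the proportion returned by week 54 and λ = −ln(1 − p) / 54 per week. Count from randomisation, taking absence before randomisation as equal on average in the groups compared.

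- Mean over all patients, counted to week 54: p / λ
- Mean among returners only: 1/λ − 54(1 − p)/p

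| p | 1/λ (weeks) | All patients (weeks) | Returners only (weeks) |
|---|---|---|---|
| 0.9 | 23.45 | 21.11 | 17.45 |
| 0.8 | 33.55 | 26.84 | 20.05 |
| 0.7 | 44.85 | 31.40 | 21.71 |
| 0.6 | 58.93 | 35.36 | 22.93 |

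Differences between arms, times 5 working days:

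| Returned by week 54 | All patients | Returners only | Share of difference lost |
|---|---|---|---|
| 80% v 60% | 8.52 weeks = 42.6 days | 2.88 weeks = 14.4 days | 66% |
| 90% v 70% | 10.29 weeks = 51.4 days | 4.26 weeks = 21.3 days | 59% |
| 70% v 60% | 3.96 weeks = 19.8 days | 1.22 weeks = 6.1 days | 69% |

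In all three scenarios the arm with fewer returns still looks worse, but by much less than it should.

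**The case against.** The strongest defence is that days lost is one descriptive line in one of eight secondary outcomes, qualified in the plan itself as reported where applicable. Non-returners are not hidden: the returned counts and the at-work or off-work counts are given by arm, and the tested comparison is of work status. A patient still off work at week 54, or newly off work at a visit, is visible there. This stands, and it limits the weight of the point. What the counts cannot show is the length of absence, or an absence that begins after baseline and ends before a visit.

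The health economic analysis also considers time off work (Protocol 8.4.2), and the COMI asks about days of work incapacity over the past 4 weeks (SAP 17.4.7.1). Neither alters the derivation in 17.4.8.1.

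A reader might infer more than the documents support:

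- **That treatment failures make an arm look better.** The general effect is attenuation. Reversal needs the arm with more non-returners to have faster returners as well.
- **That job loss drops out of the tested comparison.** The restriction to employed patients is attached to summary items. The chi-square sentence names no denominator, so it is unspecified, and job loss would appear in the employment counts.
- **That the unadjusted chi-square breaks a protocol commitment.** Protocol 9.6 says "Analysis of secondary outcomes will use similar methods, with logistic regression analyses used where appropriate", which leaves room for judgement.
- **That counting from the stop date biases the comparison.** Days before randomisation are balanced in expectation among all patients off work at baseline. They mainly add level and noise.
- **That a full count needs only data already held.** Protocol 8.1 mentions a date of returning to work on Form 4, and Table 3 schedules return to work at weeks 18 and 54. Nothing shows that dates are recorded for absences starting after baseline.

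**Conclusion.** The point holds for the derivation of work days lost. As written, the mean by arm describes only patients who were off work at baseline and came back, does not respond to the share who never return, and leaves out absence starting after baseline. With similar return times among returners, it understates days lost more in the arm with more non-returners.

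Under assumed constant return rates, between 59% and 69% of the true difference disappears in the three scenarios above; at 80% v 60% it falls from about 43 to about 14 working days. These sizes rest entirely on assumed return rates and on the constant-rate model. The direction of the omission follows from the SAP text alone.

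The primary outcome is unaffected, and the tested work-status comparison does not use this derivation. This is a correction worth making to a descriptive secondary summary and no threat to the trial's main conclusions.

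**What to change.** In SAP 17.4.8.1, for patients off work at baseline, count working days lost from randomisation to return. Patients who have not returned are counted to week 54, or censored at last contact if lost earlier. In 17.4.8.2, report by arm a restricted mean to week 54 or a Kaplan-Meier time to return, with the number not returned. Report days lost before randomisation separately.

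Check whether Form 4 or the resource-use questions hold dates or durations for absences that start after baseline. If they do, include those absences and give zero days to employed patients who were never off work. If they do not, label the summary as limited to patients off work at baseline.

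Report and compare work status at 18 and at 54 weeks separately, since the present wording leaves the time point open, and state the denominator.

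For patients off work at baseline, the cost is SAP wording and some programming. The drawback is a censoring assumption for patients lost before week 54: if those lost are less likely to have returned, days lost will still be understated, so the number censored should be shown by arm.

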#### **17.4.8.2 Analysis**

Firstly, a summary of the following will be presented:

- number of patients that are employed/not employed at each time point by treatment group (Baseline, week 18 and week 54)
- of those patients who are employed, the number of patients that are off work/at work by treatment group
- of those patients who are employed and unable to work, the number of patients that returned to work at 18 and 54 weeks
- Mean, SD, median, IQR and range of the work days lost where applicable

Secondly, work status (at work or off work) at 18 or 54 weeks post randomisation will be compared between groups using a chi-square test. The chi-square statistic and p-value will be presented. In addition to this, the relative risk and 95% confidence interval will be presented.

### **17.4.9 Cost-effectiveness, expressed as the incremental cost per quality-adjusted life-year (QALY) based on the EQ-5D-5L**

#### **17.4.9.1 Derivation**

This is a health outcome and will not be discussed in the SAP as the analyses will be undertaken by the trial health economist.

#### **17.4.9.2 Analysis**

This will be included in the health economic SAP as mentioned in section 19 [13].

## 18 Missing data and withdrawals

The numbers (with reasons) of losses to follow-up and withdrawals over the course of the trial will be summarised by treatment arm. The primary outcome is ODQ score at 18 weeks post-randomisation so if a patient withdraws after 18 weeks they will still contribute towards the primary analysis, given that consent to use all existing data collected up to that point is not removed.

The number of patients with missing data for the primary outcome and each secondary outcome will be presented in a table along with percentages.

Sensitivity analyses will be carried out if the amount of missing data is greater than 10%. Multiple imputation will be used to assess the robustness of the analysis to missing primary outcome data. The multiple imputation method will follow the guidelines set out in Jakobsen et al [14]. PROC MI in SAS will be used to generate 50 complete data sets. The imputation model will include all variables included in the primary outcome analysis model (treatment group, centre and baseline ODQ), and also ODQ measured at additional time points. The random seed for the imputation process will be pre-specified as 753. The complete data sets will be analysed using the model specified in section 17.4.1.2, and the results of all models combined using PROC MIANALYZE. The overall summary adjusted mean difference will be presented with 95% confidence intervals, to assess the sensitivity of the primary analysis to missing data.

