### 9.4.2 Revised sample size

The original sample size calculation did not assume any correlation between baseline and follow-up ODQ scores, as no data was available to estimate this. Based on a blinded analysis of the correlation between baseline and follow-up ODQ scores in the first 47 trial participants to have outcome data available, we can estimate this correlation as 0.49.

Using this estimate, our revised sample size to achieve 90% power is 66 per group. Allowing for 10% loss to follow-up gives a revised target of 74 per group (148 total).

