## 17. **Efficacy Evaluations**

### 17.1. **Data Sets Analysed**

The principle of intention-to-treat, as far as practically possible, will be the main strategy of the analysis adopted for the primary outcome and all the secondary outcomes. These analyses will be conducted on all randomised participants, in the group to which they were allocated, and for whom the outcome(s) of interest have been observed/measured.

The membership of the analysis set for each outcome will be determined and documented and reasons for participant exclusion will be given.

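### SAP 18 makes the protocol's unconditional multiple imputation depend on an undefined figure of more than 10% missing, and the SAP omits the protocol's blinded review of reasons for missingness.

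*SAP*

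**What the plan says.** Protocol 9.6 makes two commitments on missing 18-week ODQ scores.

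- A sensitivity analysis with no trigger: "Sensitivity analyses will be carried out using multiple imputation to assess the robustness of the analysis to missing primary outcome data".
- A review of reasons: "Reasons for missing primary outcome data will be assessed, blind to treatment allocation, as to whether they are informative of likely outcome". Its stated consequence is "Participants with non-informative reasons for missingness will be excluded from the primary analysis set".

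The SAP treats both differently.

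- SAP 18 adds a condition: "Sensitivity analyses will be carried out if the amount of missing data is greater than 10" per cent. It does not say whether the amount is overall or per arm. It also does not say whether it counts questionnaires that SAP 17.4.1.1 excludes as outside 18 ± 6 weeks or as having fewer than 8 of 10 items answered.
- SAP 17.1 analyses participants "for whom the outcome(s) of interest have been observed/measured" and adds "The membership of the analysis set for each outcome will be determined and documented and reasons for participant exclusion will be given". SAP 18 adds "The numbers (with reasons) of losses to follow-up and withdrawals over the course of the trial will be summarised by treatment arm". Reasons are therefore listed, but nowhere classified as informative or not, and nowhere assessed blind.

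SAP 5 states that its analyses comply with protocol version 7.0, and the SAP change control lists no change to section 18. Protocol 9.4.2 uses the same 10% as its allowance for loss: "Allowing for 10% loss to follow-up gives a revised target of 74 per group (148 total").

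**The concern.** The trial is open-label with a patient-reported primary outcome, so knowledge of the allocation could affect who returns the 18-week questionnaire. The protocol's answer was a robustness check that always runs and a blinded look at the reasons. Under the SAP, the check depends on a threshold set at the loss rate the design expects, so whether it runs at that rate is largely chance. Because the amount is undefined, the decision could also turn on a reading chosen after the data are seen.

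The review matters for a second reason. The planned imputation uses treatment, centre, baseline ODQ and ODQ at other time points, so it assumes data missing at random. The review is the only step in either document that asks whether that assumption is reasonable, and the SAP leaves it out.

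**Working it through.** **Inputs.** Difference 10 points, SD 20, 5% level, 90% power (protocol 9.4); two-sided tests (SAP 12); 1:1 allocation (SAP 8.10); correlation 0.49, 66 evaluable and 74 recruited per group (protocol 9.4.2); trigger above 10% (SAP 18).

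**The plan's own figures.** A two-sample t-test calculation gives 85.03, so 86 per arm and 172 in total, as stated. Adjusting for baseline: 86 × (1 − 0.49²) = 86 × 0.7599 = 65.4, so 66 per group. Allowing for loss: 66 / 0.9 = 73.3, so 74 per group and 148 in total. The sample size reproduces.

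**Where the trigger falls, if the rate is overall.** 14/148 = 9.5% does not fire it; 15/148 = 10.1% does. The check therefore needs at least 15 missing.

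**Chance that it is skipped.** Taking losses as independent with a common rate p, P(skipped) = P(X ≤ 14) for X binomial(148, p):

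| True loss | Check runs | Check skipped |
|---|---|---|
| 5% | 0.8% | 99% |
| 8% | 21% | 79% |
| 9% | 35% | 65% |
| 10% | 52% | 48% |
| 12% | 79% | 21% |
| 15% | 97% | 3% |

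**Why the definition matters.** Per arm, 7/74 = 9.5% does not fire the trigger and 8/74 = 10.8% does. Fourteen missing, split 10:4, would run the check on a per-arm reading (10/74 = 13.5%) and skip it on an overall one (9.5%). Similarly, 13 patients with no ODQ plus 3 excluded for timing or incompleteness are 8.8% or 10.8% (13/148 or 16/148), depending on what counts.

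**What could go unchecked (assumed scenarios).** Suppose missing patients' true mean ODQ differs from that of observed patients in the same arm by d, with the same d and direction in both arms. Ignoring any correction through baseline, an observed-case difference is off by d × (m₁ − m₂)/74, where m₁ and m₂ are the numbers missing per arm. With 14 missing:

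| Split | d = 5 | d = 10 | d = 20 |
|---|---|---|---|
| 7:7 | 0 | 0 | 0 |
| 10:4 | 0.4 | 0.8 | 1.6 |
| 14:0 (extreme) | 0.9 | 1.9 | 3.8 |

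**Scale for comparison.** With 67 evaluable per arm, SE = 20 × √(1 − 0.49²) × √(2/67) = 3.01, so the expected 95% CI half-width is 1.96 × 3.01 = 5.9 points.

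**The case against.** A reader might infer that a trial running to plan would never carry out the check. The documents do not support that. Exactly 66 evaluable of 74 per group leaves 148 − 132 = 16 missing, or 10.8%, which fires the trigger; at a true 10% loss it fires slightly more often than not. Skipping becomes near certain only at about 5% loss, where less is at stake. If out-of-window or incomplete questionnaires count as missing, the trigger is easier to reach.

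A reader might also infer that omitting the review is what removes every patient without an ODQ from the analysis. It is not: protocol 9.6 itself confines the primary set to participants with an 18-week score, and never says how an informative case would enter the model. Restoring the review alone would therefore add no defined analysis. That gap begins in the protocol.

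Three further points carry weight.

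- Imbalance between arms would not be invisible, because SAP 18 tabulates losses and reasons by arm. Only the trigger could miss it.
- The 14:0 split is a bound, not a forecast. If 14 losses fell at random among 148, the chance of all being in one arm is 2 × C(74,14)/C(148,14), about 0.00006. No document supports a 20-point gap.
- Other safeguards exist. Protocol 8.1 allows postal and, exceptionally, telephone collection at week 18. SAP 17.4.2.2 fits an unconditional repeated-measures ODQ model that can use patients with later scores only.

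None of this replaces the missing step. The repeated-measures model also relies on missing at random and, where an interaction is kept, reports differences at weeks 30, 42 and 54, not 18. The covariate-adjusted analysis in SAP 19 does not address missing data.

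**Conclusion.** The point holds as a departure of the SAP from the protocol. An unconditional sensitivity analysis has become conditional on an undefined amount, the blinded review has no counterpart, and SAP 5 nevertheless claims compliance. The conclusion rests on the text and needs no assumption about the data.

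Its practical size does rest on assumptions. With independent losses and an overall rate, the check is skipped with probability of about 48% at 10% loss, 79% at 8% and 99% at 5%, leaving up to 14 missing patients unexamined. The possible shift is about 1.6 points for a 10:4 split with a 20-point gap in both arms. It is 0.9 to 3.8 points in the extreme one-arm case with gaps of 5 to 20. All of these are below the expected CI half-width of 5.9, so they would matter mainly for a borderline result. The documents give no ground for expecting a particular bias. They show only that the promised check on one may not be made.

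**What to change.** 1. In SAP 18, delete the condition of more than 10%, so that the multiple imputation of the 18-week ODQ is always run and reported beside the primary analysis. This also removes the need to define the amount.
2. Restore the blinded review of reasons in the SAP: who assesses them, that they do so without knowledge of allocation and before the analysis, and how each reason is classed as informative or not.
3. Because the planned imputation assumes missing at random and neither document says how informative cases would be analysed, add a simple delta-adjusted imputation as their sensitivity analysis, shifting imputed 18-week scores by arm. The shift sizes are for the sponsor to choose and should be fixed in advance.

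If the sponsor prefers to keep a threshold, the protocol should be amended with a reason and the amount defined.

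The cost is a few SAP sentences and extra PROC MI runs. No new data are needed and the sample size does not change.
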